ASSIST	The Alcohol, Smoking, and Substance Involvement Screening Test
BSI	Brief Symptom Inventory
CAI	Condomless Anal Intercourse
CASI	Commuter Assisted Self-Interview
CDC	Centers for Disease Control and Prevention
CLIA	Clinical Laboratory Improvement Amendments
CRF	Case report form
DAIDS	Division of AIDS
GCP	Good Clinical Practices

HIV	Human Immunodeficiency Virus
ICH	International Conference on Harmonization
IGHID	Institute for Global Health & Infectious Diseases
IRB	Institutional Review Board
MSM	Men who have sex with men
NIH	National Institutes of Health
NIMH	National Institute of Mental Health
PI	Principal Investigator
PrEP	Pre Exposure Prophylaxis
OHRP	Office of Human Research Protection
RCT	Randomized controlled trial
RNA	Ribonucleic acid
SAE	Serious adverse event
SCT	Social cognitive theory
SID	Study ID number
SMART	Study Management and Retention Tool
SOC	Standard of care
SRV	Study Recruitment Venue
SSL	Secure Socket Layer
UNC	University of North Carolina
US	United States
VAS	Visual analogue scale
VBI	Virtually Better, Inc.
VL	Viral Load

VR Virtual Reality

[figure not shown]
YMSM Young men who have sex with men

Study Abstract

Protocol Title	Tough Talks - Virtual Support for Difficult Conversations: Using Artificial Intelligence to Increase HIV Disclosure Among Young Men Who Have Sex With Men
Design	
This study includes 2 phases:
 
Phase 1: a technical pilot to optimize functionality and technical performance; and
 
Phase 2: a three-arm RCT to evaluate efficacy and effectiveness of Tough Talks among HIV-positive YMSM.

Intervention Description	Tough Talks is an application (app) for smartphones or tablets for young men living with HIV to learn about and practice HIV disclosure in a safe space. Tough Talks helps young men living with HIV to think about and practice disclosing. The app includes four sections (Understanding disclosure; Should I disclose? How do I disclose?; Preparing for the outcome) with information about disclosure, activities to encourage YMSM to think about their own disclosure values and style, choose your own adventure style games, and virtual reality scenarios for them to practice disclosing their status safely.
Protocol Duration	24 weeks for Phase 2
Sample Size	We will recruit approximately 210 YMSM (8-16 in Phase 1; 198 in Phase 2) across 6 study sites (Chapel Hill, NC; Houston, TX; Tampa, FL; Bronx, NY; Atlanta, GA; Charlotte, NC) that have extensive experience engaging, enrolling and retaining HIV-positive YMSM. For Phase 2, we will also recruit and enroll YMSM nationwide to participate remotely.
Population	1) age 16-29 years; 2) assigned male sex at birth; 3) male-identified; 4) HIV positive; 5) owns and has reliable access to a mobile device (smartphone) or tablet; 6) able to understand, read, and speak English; 7) reports ≥ 1 episode of anal intercourse with a male partner in past 6 months OR reports a sexually transmitted infection (STI) diagnosis in the last six months; 8) For RCT only: have a viral load measurement within 12 months prior to enrollment (or on day of enrollment). As this is a minimal risk study, we will use a waiver of parental consent for YMSM under age 18.
Data Collection	During the piloting and RCT stages, YMSM will complete computer-assisted self-interviews (CASI). Pilot trial participants and a sub-set of RCT intervention participants will complete a post-intervention qualitative interview. During the RCT, data will also be collected via chart review. Audio recorders will be used to record the content of the discussions during the qualitative interviews.

	
The data collected from individuals will be stored using a numerical system to identify each subject. Only the staff working on this study will have access to the records and identities of the subjects. This includes the Principal Investigators, Co-Investigators, and additional members of the research team.

Objectives	
1. A technical pilot to optimize functionality and technical performance.2. A three-arm RCT to evaluate efficacy and effectiveness of Tough Talks among HIV-positive YMSM.
Outcomes	
Primary outcome: Viral load (VL) suppression defined as HIV RNA < the lower limit of detection as per the laboratory at each clinical site.
 
Secondary outcomes: We will also assess intervention efficacy on a panel of self-reported outcomes including sexual risk, STI infections, disclosure behaviors, intentions and self-efficacy.

Number of sites	6 in-person (Houston, TX; Bronx, NY; Tampa, FL; Chapel Hill, NC; Atlanta, GA; Charlotte, NC); nationwide recruitment for remote procedures
Clinical Samples	Viral load suppression: Viral loads will be assessed through chart review, blood draw, or participant shared documentation at baseline, 3 and 6 months. Participants with no VL result in their medical record in the 2 months prior to or 3 months after their 6-month follow up visit will have one drawn for the study. Participants may also self-report viral load at 6 month. Viral load suppression will be defined as HIV RNA < lower limit of detection as per the laboratory processing the sample.

Phase 2 (RCT) Study Schema

1.0 INTRODUCTION

1.1. Background

Men who have sex with men (MSM) account for nearly two-thirds all of new HIV diagnoses in the United States (US) and young MSM (YMSM) continue to be disproportionately affected¹. Among youth living with HIV, 67 percent report not disclosing to their first-time sex partners². Disclosing of one's HIV status is important for accessing support which can lead to improved medication adherence and retention in care. Those who disclose are more likely to use condoms with HIV-negative sex partners³ and mathematical modeling estimates that increased HIV status disclosure to sex partners may reduce transmissions by 40-60%^{4,5}. Further, disclosure may motivate HIV-negative sex partners to seek testing and reduce their own HIV transmission behaviors. Given the potential benefits and challenges associated with disclosure, there is a need for sophisticated interventions that can assist MSM with the disclosure process. Virtual reality provides a unique environment for users to practice HIV disclosure. Artificial intelligence (AI) driven disclosure may offer advantages over in-person role play through the use of realistic avatars that represent potential romantic partners, and probabilistic settings where users envision having disclosure conversations. Users have the opportunity to practice disclosing and experience a variety of responses and outcomes. During Phase I of this project we developed an iPad-based virtual reality system that features three avatars, two virtual locations and three disclosure scenarios which represent a variety of common disclosure experiences and contexts experienced by YMSM⁶. In Phase II, we will further enhance **Tough Talks** and develop a full-feature automated version to test via a multi-site, randomized controlled trial (RCT).

1.2. Rationale

HIV status disclosure is a stressor in the lives of many HIV-positive persons⁷. Failure to disclose HIV status can negatively impact health, impeding adherence to care or medications and hindering reduction of sexual risk behaviors^{8,9}. Moreover, individuals who fail to disclose miss the positive effects of post-disclosure support^{9,10}. Disclosure to sexual partners, friends, and family can lead to social support, closer relationships, antiretroviral therapy (ART) initiation, adherence, and improved psychological well-being^{9,11}. Notably, one study of 373 HIV-positive patients in Seattle found an independent association between disclosure of HIV and increased CD4 T-cell counts over time¹². A study by Kalichman et al. found that among 538 sexually active HIV+ MSM, engaging in sex without a condom with undisclosed non-concordant partners was associated with worse ART adherence and greater likelihood of unsuppressed HIV¹³.

Among MSM, many studies have found that disclosure of HIV status leads to a reduction in sexual risk^{14,15} and increased social support^{9,10}. Most data show that individuals who can communicate with sex partners about sexual health topics, including disclosure of HIV status, are more likely to engage in condom use behaviors¹⁴⁻¹⁷. Furthermore, disclosure may motivate sex partners to seek HIV testing and reduce their own HIV transmission behaviors, as well as influence other risk-reduction strategies such as strategic positioning (choosing insertive or receptive anal intercourse based on serostatus), serosorting (limiting sexual partners to those of the same serostatus) and the use of pre-exposure prophylaxis (PrEP)¹⁸⁻²⁰.

Stand-alone eHealth interventions are potent tools for public health. Unlike traditional in-person interventions, stand-alone eHealth interventions are not limited by cost or availability of interventionists to deliver them. Further, eHealth interventions are scalable and accessible, especially for youth who engage with technology on a regular basis and are early adopters²¹. In addition, eHealth interventions have the potential to be customizable to the unique participant based on user input.

Virtual Reality (VR) has great potential as an educational tool by offering participants a safe, situated learning space where they can learn-by-doing and problem solve in a realistic environment that enables the transfer of skills learned in VR into real life²²⁻²⁴. VR allows participants to practice disclosing to realistic virtual characters that represent potential romantic partners, as well as in realistic settings. Participants have the opportunity to practice disclosing using a variety of strategies and experience different outcomes including acceptance, confusion, lack of HIV knowledge, and rejection.

VR is a technological tool that can be used to enhance learning by eliciting participant emotions and invoking affective experiences through interaction with its contents. It provides several key advantages over current methods of delivering HIV prevention interventions, such as role-play and video vignettes²⁵. Specifically, the sensory-rich, immersive environments of VR (virtual characters, visual ambience, directional audio, culturally specific content) provide a realistic avenue for YMSM for mental rehearsal and performance of HIV disclosure behaviors in a controlled environment where new challenges can be gradually introduced. Further, VR environments provide a standardized setting that can be controlled and replicated to deliver the intervention in a systematic manner. Additionally, incorporating interactivity and game mechanics (e.g. customizable virtual characters, virtual conversations) is highly innovative and will provide participants with a compelling, engaging experience that will motivate and support behavior change.

Scientific Premise: Disclosure impacts adherence in care, viral suppression, HIV transmission and mental and physical health. There are no stand-alone sexual partner disclosure interventions, much less any that can be delivered wholly online. **Tough Talks**, a VR HIV disclosure intervention, shows the potential for theoretically backed VR interventions to work as a tool to build self-efficacy. A similar strategy could be applied to other topics that impact an individual's health and wellbeing - from coming out about one's sexual or gender identity, to training doctors to improve delivery of difficult diagnoses, and to helping their patients learn to talk with their families about a variety of medical conditions.

Table 1: Description of Tough Talks application

Module	Description	List of Activities
Understanding Disclosure	Participants go through activities that set up what it means to disclose your HIV status, while reminding them that they are not defined by their status and that disclosure is a choice. Activities in this module include exercises about disclosure laws across the country, thinking about different situations in which you may have to disclose or not (to an employer? To a roommate? To a sex partner? Etc.), and a mock texting activity	
• Choose your own adventure: It's Like Coming Out...Again• What is disclosure? (video)• Disclosure and the Law• Do I have to disclose if...• HIV doesn't change who I am• Disclosure Advice• Virtual Disclosure Practice

	where they give advice about disclosure to a friend.	
Should I disclose?	Participants are led through a series of activities that model different ways to think about and decide if they want to disclose to someone. Activities in this module include reviewing a list of items and assigning them as pros or cons of disclosing, and thinking about the right time and place to disclose.	
• Choose your own adventure: Learning the Ropes• Past Disclosure Experiences• To disclose, or not to disclose?• Disclosure experience videos• Right Time, Right Place• Virtual Disclosure Practice
How do I disclose?	Participants are presented with different ways to disclose to someone and encouraged to think about what ways feel best to them. Activities in this module include reviewing different ways to go about disclosure, and what disclosure can look like depending on what feels right to the participant.	
• Choose your own adventure: He Likes Me...He Likes Me Not• Ways to Tell Someone• Texting Disclosure• Would I say that? Conversation Starters• How to Deal with Someone Finding Out• Virtual Disclosure Practice
Preparing for the outcome	Participants explore activities that help them think about the outcome after disclosure, from receiving support, to how to handle a poor reaction. Participants are reminded that they aren't responsible for how others respond. Activities in this module include reviewing a list of commonly asked questions and answers (ex. Is there anything I can do to protect myself? What does undetectable mean?) and thinking about what they feel comfortable answering.	
• Choose your own adventure: Worst Case Scenario• Are You Prepared for the Questions?• After you tell them. What are you willing to answer?• How Would YOU answer?• What am I most afraid of?• How to exit "gracefully" if things go awry• Virtual Disclosure Practice

2.0 STUDY OBJECTIVES

2.1 Primary Outcome

The primary outcome is viral load (VL) suppression. Viral load suppression will either be obtained by chart review, or drawn for the study. Viral load suppression will be defined as HIV RNA < the lower limit of detection as per the laboratory processing the sample.

2.2 Secondary Outcomes

We will also assess intervention efficacy on a panel of self-reported outcomes including condomless anal intercourse (CAI), STI infections, and disclosure behaviors, intentions and self-efficacy. For binary outcomes, we define intervention efficacy as a difference in proportions, while for continuous outcomes, we define efficacy as a difference in means. (See Table 2 on page 45)

2.2.1 Cost Outcomes and Cost Effectiveness

To compare costs between the intervention arms, we will collect information on (1) time spent by study staff for training and supervision of delivering the clinic VR intervention; (2) time participants spend in the clinic sessions; and (3) costs associated with the delivery of both home and clinic arms. The procedures we will use to quantify the resources required to deliver the interventions will be organized in standard expenditure categories: personnel, supplies, equipment, services, space, and overhead. Incremental cost effectiveness ratio between the 2 intervention arms will be defined as $\Delta C/\Delta E$, where ΔC denotes the estimated difference in mean costs of the intervention and ΔE reflects the estimated difference in mean effectiveness of proportion suppressed between the interventions.

2.3 Hypothesis

We have the following hypotheses:

- A. Participants in both intervention arms will be more likely to be virally suppressed at 6 months compared to participants in the SOC arm.
- B. Participants in both intervention arms will report less CAI with potentially susceptible partners at six months compared to participants in the SOC arm.
- C. Participants in Arm 2 (clinic) will report greater intervention satisfaction and immersion but Arm 2 will be costlier.

3.0 STUDY DESIGN

This study includes 2 phases:

- 1) A technical pilot to optimize functionality and technical performance of the intervention; and
- 2) A three-arm RCT to evaluate efficacy and effectiveness of **Tough Talks** among HIV-positive YMSM.

3.1 Study Population

The total study sample is approximately 210 YMSM, of which the following will be enrolled for each phase: 1) a technical pilot will be conducted with 8-16 HIV+ YMSM in North Carolina; 2) and an RCT will be conducted with 198 HIV+ YMSM by study staff at 6 study sites (Houston, TX; Bronx, NY; Tampa, FL, Chapel Hill, NC; Atlanta, GA; Charlotte, NC). For the RCT phase, participants may also be enrolled remotely from any state in the United States.

3.2 Sample Size

We will recruit approximately 210 YMSM (8-16 in Phase 1; 198 in Phase 2). To ensure inclusion of diverse youth who are representative of the US epidemic, we will attempt to oversample YMSM of color, with a goal of enrolling two-thirds of the cohort YMSM of color.

3.3 Study Randomization, Stratification, or Description of Non-Random Assignment Procedures

Technical Pilot: Participants will be recruited from UNC-Chapel Hill. We will enroll 8-16 participants. After participants are consented, they will complete a web-based computer assisted survey instrument (CASI) using Qualtrics software. Participants will be randomized to either use Modules 1 and 2 or Modules 3 and 4. Participants will receive a short orientation to the program before use. Participants will be provided with a notebook to take notes on each activity, as well as take a survey on each activity. At the end of each module, participants will do a short qualitative semi-structured interview. At the end of the second module, they will take a post survey. They will receive \$75 for their participation in this aim of the study. Participants can choose to re-enroll and complete the other two Modules of Tough Talks as well.

RCT: Participants will be recruited from across the country. We will enroll a total of 198 participants. After participants are consented, they will complete a baseline web-based computer assisted survey instrument (CASI) survey using Qualtrics software and be randomized in a 1:1:1 fashion into one of three arms: 1) the Tough Talks fully-online intervention, 2) the Tough Talks clinic-based intervention or 3) the SOC control condition, based on a randomization sequence developed by UNC and administered through REDCap. The randomization sequence will be stratified by study site. Participants may enroll in-person or remotely via video teleconferencing system.

4.0 SELECTION AND ENROLLMENT OF PARTICIPANTS

4.1 Inclusion Criteria

Inclusion Criteria for All Aims

- Age 16-29 years
- Assigned male sex at birth
- Born male and male-identified
- Able to understand, read, and speak English

Additional Criteria for Technical Pilot:

- Reports ≥ 1 episode of CAI with a male partner in past 6 months
- HIV-positive (self-report)

Additional Criteria for RCT:

- HIV-positive (medical chart review)
- Viral Load measure within 12 months of screening date (assessed by chart review, blood draw, or shared by participant via video teleconferencing or Qualtrics)
- Owns and has reliable access to a smartphone or tablet
- Has reliable internet access
- Reports ≥1 episode of anal sex with a male partner in past 6 months (self-report) OR reports STI diagnosis (urethral/rectal gonorrhea or chlamydia or syphilis) in the last six months (self-report OR medical chart review)

As this is a minimal risk study, we will seek a waiver of parental consent for YMSM under age 18 (see Human Subjects section).

4.2 Exclusion Criteria

Exclusion Criteria for All Aims:

- Under 16 years of age
- Over 29 years of age
- Assigned female at birth
- HIV negative
- Reports 0 episodes of anal sex with a male partner in the last 6 month AND reports no new STI diagnosis (urethral/rectal gonorrhea or chlamydia or syphilis) in last 6 months.
- Currently enrolled in another HIV behavioral intervention study; previous or future enrollment in another HIV behavioral intervention study is permissible, as is participation in any standard of care intervention(s) within the clinical study site.

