5.4 Intervention/Investigation Procedures

5.4.2 Technical Pilot

After development is complete and internal beta testing performed, both the Tough Talks intervention and intervention procedures will be evaluated and revised during a technical pilot with a small group of YMSM participants (8-16) at one site (Chapel Hill, NC). All participants will be given brief instructions on the purpose of Tough Talks and an overview of how to use the program. They will complete an online assessment at baseline and a post survey after using the program. Participants will also be asked to provide feedback during qualitative interviews conducted by study on intervention content, functionality, technical performance, errors and bugs encountered, overall experiences using Tough Talks, and feedback for further refinement. We will solicit feedback about the acceptability and utility, and assess how the intervention components could be strengthened, identifying areas needing improvement for future iterations. Participant feedback will be specifically sought on the subjective impact of the intervention on HIV disclosure, engagement in care and ART adherence. Participant feedback will also be solicited on the acceptability of the assessments with respect to duration and relevance. Both the qualitative and quantitative data from the technical pilot will be used to refine the Tough Talks program, the intervention protocol and the assessment tools prior to the RCT pilot (Aim 3) using a concurrent triangulation approach, taking advantage of the strengths of both data types to cross validate results.⁶² These data will be used to further refine the intervention protocol and instruments to be tested in the pilot RCT (Aim 3).

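### The RCT criteria do not exclude men who used Tough Talks in the technical pilot, so a pilot man who qualifies can be randomised to SOC; the effect is small and cheap to prevent

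*Combined protocol and SAP*

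**What the plan says.** Section 4.2 gives a single list, headed "Exclusion Criteria for All Aims", with no separate exclusions for the RCT. Its only clause on other research reads: "Currently enrolled in another HIV behavioral intervention study; previous or future enrollment in another HIV behavioral intervention study is permissible". The inclusion criteria in 4.1 contain no condition on prior exposure. The text on recruitment, screening, enrolment and randomisation (4.3, 4.5, 5.1, 5.3, 5.4.3, 6.1, 6.2) adds none.

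On the pilot, section 3.1 states that "a technical pilot will be conducted with 8-16 HIV+ YMSM in North Carolina", and 5.4.2 places it at Chapel Hill. Section 5.4.3 lists Chapel Hill among the six RCT sites. Section 3.3 describes the exposure: "Participants will be randomized to either use Modules 1 and 2 or Modules 3 and 4". It then adds: "Participants can choose to re-enroll and complete the other two Modules of Tough Talks as well". Section 10.2.2 describes the pilot app as nearly final.

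**The concern.** A pilot man has already worked through half or all of the module content that the RCT tests. If he is later assigned to SOC, he is an exposed control, and the difference between SOC and each intervention arm shrinks.

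The planned analyses would not reveal or repair this. The primary analysis in 10.3.3 is by intention to treat and keeps him in SOC. The sensitivity analyses in the secondary analysis plan concern completion of the intervention as delivered in the trial, which says nothing about exposure before randomisation. No field that records prior use is described.

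A second route affects the continuous secondary outcomes, such as disclosure self-efficacy and intentions. These are modelled as change from baseline to six months. For a pilot man in any arm, that baseline already follows exposure.

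**Working it through.** **Step 1. Can a pilot man qualify?** Age, sex, gender identity and language criteria are common to both phases (4.1). The pilot requires condomless anal intercourse in the past six months, which also meets the RCT's anal-sex criterion if it still holds at RCT screening. He must further have chart-confirmed HIV (self-report suffices for the pilot), a viral load within 12 months, a smartphone or tablet, and internet access. A man who meets these is eligible.

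**Step 2. Does the clause in 4.2 stop him?** If the pilot is *another* study, the clause lets him in once he has finished it. If the pilot is part of the same study, the clause does not apply and no other rule does. Neither reading excludes him.

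**Step 3. Reproduce the plan's sample size.** Inputs from 10.2.3: 0.66 versus 0.88, two-sided alpha 0.05, 80% power, 15% loss, 66 per arm. The plan gives 0.66 as the baseline rate; I assume SOC stays there at six months. With pooled variance under the null:

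n = [1.96·√(2p̄q̄) + 0.842·√(p₁q₁ + p₂q₂)]² / (p₂ − p₁)², where p̄ = 0.77

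= [1.96·√0.3542 + 0.842·√0.33]² / 0.22² ≈ 56.3, so 57 evaluable per arm.

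57 × 1.15 = 65.6, which rounds up to the plan's 66. (57/0.85 gives 68.) Conversely, 66 × 0.85 = 56 evaluable, and

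power = Φ{[0.22·√56 − 1.96·√0.3542] / √0.33} = Φ(0.835) = 79.8%.

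**Step 4. Dilution of the primary contrast.** Let k pilot men enrol and let c be the share of the 0.22 effect that each carries over. Under 1:1:1 allocation, k/3 are expected in SOC, a share f = (k/3)/66. Then

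SOC rate = 0.66 + 0.22·c·f, and RD = 0.88 − SOC rate.

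Only SOC men enter f. In this model a pilot man in Arm 1 or 2 still has the 0.88 probability, so he does not change the six-month difference.

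| k | c | Expected in SOC | SOC rate | RD | Power, 56 per arm |
|---|---|---|---|---|---|
| 0 | – | 0 | 0.660 | 0.220 | 79.8% |
| 4 | 50% | 1.3 | 0.662 | 0.218 | 79.1% |
| 8 | 50% | 2.7 | 0.664 | 0.216 | 78.4% |
| 16 | 50% | 5.3 | 0.669 | 0.211 | 76.9% |
| 8 | 100% | 2.7 | 0.669 | 0.211 | 76.9% |
| 16 | 100% | 5.3 | 0.678 | 0.202 | 73.8% |

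For the last row: f = 5.33/66 = 0.081, SOC rate = 0.66 + 0.22 × 0.081 = 0.678, RD = 0.202.

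**Step 5. Secondary scales.** The documents give no standard deviation or expected change for these outcomes, so the effect of a post-exposure baseline cannot be sized.

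**The case against.** The best case against is that this hardly matters. The pilot has at most 16 men. Section 5.1 describes a single in-person session, normally covering two of the four modules and used to collect feedback. Full carry-over of a 0.22 effect from that is unlikely, and not every pilot man will meet the RCT-only criteria or want to enrol. Stratifying randomisation by site also tends to spread Chapel Hill men over the arms. All of this stands, and it is why the effect is graded small.

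Several stronger readings are tempting but unsupported:

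- A reader might infer that 4.2 expressly admits pilot men. The pilot is a phase of this same protocol, so the clause may not reach it. What is certain is that no rule excludes them.
- A reader might infer that pilot men in the intervention arms also shrink the primary contrast. The primary measure is the six-month risk difference, not change from baseline, so under the carry-over model they do not.
- A reader might extend the point to users of the earlier iPad version in 1.1. That section describes a system being built and names no participants who used it.
- A reader might claim a heavy concentration in the Chapel Hill stratum. The documents set no site quotas, and remote enrollees are also assigned to sites.

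The phase totals in 3.1 and 3.2 (8–16 plus 198, approximately 210) suggest that separate men were intended, but they are counts and not an eligibility rule. A restriction stated only in the consent forms cannot be checked, since those pages were not available for review.

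**Conclusion.** The gap in the eligibility text is real: nothing keeps a qualifying pilot man out of the RCT or out of SOC. The consequence for the primary outcome is small. With 4–8 pilot men enrolling and 50% carry-over, RD is 0.218–0.216 and power falls from 79.8% to 79.1–78.4%. The figure of 73.8% (RD 0.202, about 5 exposed SOC men) requires all 16 to enrol with full carry-over and is an upper bound, not an expectation. Both uptake and carry-over are assumptions. The documents do not say that any pilot man entered the RCT. The point merits a change because prevention costs almost nothing and the intention-to-treat contrast cannot be restored once an exposed man has been randomised.

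**What to change.** Add one RCT-specific line to 4.2: *Prior use of Tough Talks, including participation in the technical pilot.* Add a matching screener item, and have the team that holds the pilot list check each enrollee against it before the REDCap assignment is drawn.

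The cost is one line, one question and one list check. At most 8–16 potential enrollees are lost, and the target of 198 is unchanged. Recording prior use at screening, with a sensitivity analysis that leaves those men out, is a workable second choice. It would make the exposure visible but leave the primary contrast diluted.
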